## Vision Loss Duration at The Time of Treatment

Vision loss duration in days will be based on the difference between the date of onset of vision loss per eye and screening date.

## ETDRS/LogMAR and on-chart and off-chart:

- I. 1 ETDRS line = 5 letters
- II. 1 ETDRS line = 0.1 LogMAR
- III. 0.1 LogMAR = 5 ETDRS letters
- IV. 15 ETDRS letters = 0.3 LogMAR

V. A less positive/more negative LogMAR is an improvement of vision

VI. An increase in the number of ETDRS letters read is an improvement of vision

On-Chart subjects: defined as being able to read at least 3 ETDRS letters on a single line on the ETDRS chart at either 4 or 1 meters

- a. Have an obtainable Snellen equivalent obtained directly from ETDRS chart
- b. Each Snellen equivalent is assigned a LogMAR value

Off-chart Subjects: defined as a subject who cannot read at least 3 ETDRS letters on a single line of the ETDRS chart at either 4 or 1 meters and thus have no Snellen equivalent obtainable from ETDRS chart

- c. These subjects are categorized as able to either count fingers (CF), detect hand motion (HM), detect light perception (LP) or are no-light perception (NLP)
- d. For those categorized as either CF or HM a method for deriving LogMAR visual acuity is pre-specified
- e. The distance at which CF/HM vision was obtained is recorded per the standard operating procedure
- f. Study database derives the LogMAR based on this distance and the finger/hand dimensions of the examiner, per pre-specified method.

[figure not shown]
#### Treatment-Emergent Adverse Events (TEAE)

Treatment-emergent adverse events (TEAEs) are defined as AEs that started after study treatment administration at Visit 3 or that represent an exacerbation of a condition that is present at baseline after treatment administration. Worsening of visual acuity determined by the investigator to be due to progression of LHON will not be considered as an AE. Any AE with an unknown start date will be considered treatment-emergent if the event does not stop prior to study treatment administration. AEs with partial dates are described in [Section 5.5.2](#)

#### Prior and Concomitant Treatment

Prior treatments will be defined as any treatments with start date and time prior to the study treatment administration date and time.

Concomitant treatments will be defined as any treatments ongoing at the start of study treatment administration or with a start date and time on or after the study treatment administration date and time. Treatments with partial dates will be dealt similarly as AEs with partial dates described in [Section 5.5.2](#). If the start time is missing, then treatments will be assigned ‘concomitant’ based on start date of treatments only if it is on or after the treatment administration date.

## **5.5 HANDLING OF MISSING DATA AND/OR INVALID DATA AND OUTLIERS**

### **5.5.1 Efficacy**

In case of missing data at Week 48, the following rules will be applied in the primary imputation method:

Rule 1: If the LogMAR is available at the previous and the following visits then the imputed value at Week 48 will be a linear interpolation of LogMAR.

Rule 2: If there is no following visit due to drop out then the relative change (RCi) from visit Vi to visit Vi+1 will be calculated at each visit from the baseline to the visit preceding Week 48 in the group treated with a sham. The last available visit (Vi) with data (Xi) will be used as the starting time point. The imputed score at Vi+1 for each eye will be equal to  $Xi+1 = Xi * RCi$ .

The imputed score at the next missing visit Vi+2 will be equal to  $Xi+2 = Xi+1 * RCi+1$ , and so on up to Week 48 visit. The RCi will be the same for the treated and sham eyes.

With the primary method of imputation, the between eye difference at Week 48 will be proportional to the between eye difference at the time of withdrawal because the same RCi coefficients are used for both eyes.

The secondary imputation method leading to an additional sensitivity analysis will apply the same Rule 1 but Rule 2 will be based on the evolution of the difference between treated and sham eye. RCi is then the relative change from visit i to visit i+1 of the difference between treated and sham eye in all subjects attending visit i and i + 1. This method assumes that the evolution of drop-out is similar in terms of between eye differences to that of subjects who were followed-up.

Other:

When a test result score/value for the Pelli-Robson Contrast test, or the Farnsworth-Munsell 100 Hue Color test is missing at any visit, for the reason that the subject was unable to perform because the vision was too poor or unable to perform within the constraints of time limitation pre-defined in the Standard Operating Procedure (for the Farnsworth-Munsell 100 Hue Color test), the following convention will be utilized: the worst possible score for the given test will be utilized as the value for that visit.

### 5.5.2 Safety

#### Missing/Partial Start Date for AEs

The following rules will be applied to missing or incomplete start dates when determining if an AE is treatment emergent. The rules will be applied first before determining the treatment emergent status and imputed dates will be treated as complete dates for this purpose. These rules are intended to lead to a conservative assessment of treatment emergence. The imputed dates are only used for determining treatment emergence and the recorded partial dates will be displayed in listings. The same rules will be applied for prior and concomitant medications as per [section 5.4](#)

If the year of onset of the AE is missing, then the AE is considered treatment emergent.

If the year of the AE onset date is complete, but the month and day of the onset of the AE are missing, then the following rules apply:

- If the year of the AE is the same as the year of the study treatment administration then the AE is considered treatment emergent, and the AE onset date will be set to the study treatment administration date.
- If the year of the AE onset date is after the year of study treatment administration, then the date is set to 01 January and the AE is considered treatment emergent.
- If the year of the AE onset date is before the year of study treatment administration date, then the AE is not treatment emergent.

If the year and month of the AE onset date are complete, but the day of the onset of the AE is missing, then the following rules apply:

- If the year and month of the AE onset date is the same as the year and month of the treatment administration date, then the AE is considered treatment emergent and the AE onset date will be set to the treatment administration date.
- If the year and the month of the AE onset date are complete, and the month of the AE onset date is after the month of the study treatment administration date, then the day of the AE onset date will be set to the first day of the month. The AE will be assigned as treatment emergent.
- If the year and the month of the AE onset date are before the year and the month of treatment administration date, then the AE is not treatment emergent.

#### Missing/Partial End Date for AEs

If the end date is missing and the start date is on or after the date of treatment administration, then the AE is considered treatment emergent

#### Missing/partial dates for prior and concomitant treatments

Missing and partial dates of prior and concomitant treatments will be dealt similarly as partial dates for AEs.

If the year and month of the medication end date are complete and there is no day value, and the month of the medication end date is on or after the month of the study treatment administration date, then the day of the medication end date will be set to the first day of the month. The medication will be assigned as prior or concomitant medication based on the imputed date.

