8.5 Prior and Concomitant Therapy

Prior therapy is defined as prescription and non-prescription medications and preparations, including health and/or dietary supplements taken within 30 days prior to signing the informed consent, but discontinued prior to signing informed consent. Concomitant therapy is defined as prescription and non-prescription medications and preparations,

health and/or dietary supplements other than GS010 IMP that the subject receives during the course of the study (i.e. any time after the signing of informed consent). This includes any medication started prior to signing informed consent and continued after signing.

Idebenone must be completely discontinued for at least 7 days prior to Visit 2 and is prohibited throughout the study. If idebenone has not been discontinued at least 7 days prior to Visit 2 and if the study protocol timeframe between the visits is respected, Visit 2 may be delayed until the 7-day period is complete.

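### A medication end date with a missing day is set to the first of the month, so a drug still in use at the injection can be classed as prior only

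*SAP*

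**What the plan says.** The rule is in SAP 5.5.2, under Missing/partial dates for prior and concomitant treatments. It applies when the year and month of stopping are known, the day is missing, and "the month of the medication end date is on or after the month of the study treatment administration date". The instruction is "then the day of the medication end date will be set to the first day of the month", and the date is put to use: "The medication will be assigned as prior or concomitant medication based on the imputed date".

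The definitions are in SAP 5.4. Any drug begun before the injection counts as prior. For the other class the SAP says: "Concomitant treatments will be defined as any treatments ongoing at the start of study treatment administration". Drugs begun at or after the injection also belong to that class. A drug begun before treatment is therefore always prior, and is concomitant as well only if it was still running at the injection.

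SAP 5.5.2 also gives the rules for partial adverse-event onset dates. If the onset falls in the treatment month and the day is missing, "then the AE is considered treatment emergent and the AE onset date will be set to the treatment administration date". Of the rules in that block the SAP says: "These rules are intended to lead to a conservative assessment of treatment emergence". It extends them to prior and concomitant medications, and the medication subsection itself opens by saying that its dates are handled like adverse-event dates.

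**The concern.** Setting a missing day to the first of the month is a convention for start dates. Applied to an end date, it gives the shortest exposure that the recorded month allows. The treatment month is the only one where, for a drug begun before treatment, the imputed day can decide status. There the rule settles the doubt against exposure, while the adverse-event rule in the same section settles it towards exposure.

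At stake is the count of subjects on each concomitant drug at and after the injection, which SAP 9.4.2 summarises for the Safety population. A second effect is on data consistency: a drug started after the injection and stopped in the same month can receive an end date earlier than its own start.

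**Working it through.** The plan gives no figure to reproduce. The check applies the end-date rule and the SAP 5.4 definitions to every case.

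**Notation.** The injection is on day *t* of the month and the true stop is on day *s* of the same month, recorded without a day. The drug started before treatment. The imputed stop is day 1.

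**Status in the treatment month**

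- *t* = 1: the imputed stop equals the treatment date, so it does not precede the injection and the problem does not arise.
- *t* ≥ 2: 1 < *t* always, so the drug is classed prior only, whatever *s* is.
  - If *s* < *t*, the drug had stopped before the injection and the class is right.
  - If *s* ≥ *t*, the drug was in use on or after the treatment day and the class is wrong. For illustration, with *t* = 10 and *s* = 25 the imputed stop is 9 days before the injection and the true stop is 15 days after it.

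**Later stop months.** Day 1 of any later month falls after the injection, so status is right.

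**Drugs started on or after the injection.** These are concomitant by start date, so status does not change. The imputed stop on day 1 precedes the start unless the drug was started on day 1.

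**How often, under an assumed calendar.** Take the treatment dates of 2016, with every pair (*t*, *s*) within a month given equal weight. The year and the weights are assumptions for illustration. Let *L* be the length of a month.

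- Treatment dates: Σ*L* = 366, of which 12 are the first of a month. The imputed stop precedes treatment on 366 − 12 = 354 dates (354/366 = 96.7%).
- All pairs: Σ*L*² = 7×961 + 4×900 + 841 = 11,168.
- Truly in use on or after the treatment day: Σ*L*(*L*+1)/2 = (11,168 + 366)/2 = 5,767.
- Of these, imputed as stopped before treatment: 5,767 − 366 = 5,401 (93.7%). With *t* ≥ 2 it is 100%.
- Truly stopped before treatment: 11,168 − 5,767 = 5,401 (48.4% of all pairs).

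**Same grid with the last day of the month.** None of the 5,767 pairs in use is imputed as stopped before treatment. The 5,401 pairs that had truly stopped are now counted as concomitant. With equal weights the number of errors is the same under either rule (5,401 of 11,168); what changes is their direction, from missed exposure to over-counted exposure.

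**The two rules side by side**

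| Partial date in the treatment month | Imputed day | Doubt settled towards |
|---|---|---|
| Adverse-event onset | Treatment date | Counting the event |
| Medication end | Day 1 | Not counting the exposure |

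**The case against.** A reader might infer a larger consequence: that a prohibited drug could look as if it stopped in time, hide a major deviation and leave the subject in the per-protocol set. Protocol 8.5 supplies the obvious case: "Idebenone must be completely discontinued for at least 7 days prior to Visit 2 and is prohibited throughout the study". Visit 2 is the day before treatment, that is day *t* − 1, so a stop meets the washout if it falls on day *t* − 8 or earlier. An imputed stop on day 1 meets this only when *t* ≥ 9. For *t* from 2 to 8 the imputed date would point to a breach rather than conceal one.

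Even for *t* ≥ 9 the documents do not support the inference. Major deviations are decided at the masked data review (SAP 9.2), and nothing ties them to the imputed date. Recorded partial dates stay in the listings under the adverse-event rules that are carried over to medications, and SAP 9.4.2 lists all medication data. The washout is checked at Visit 2 as an exclusion criterion. Idebenone started after treatment stays concomitant by its start date.

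Other objections also have force:

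- The statement about conservatism sits under adverse-event start dates and concerns treatment emergence. It reaches medications only by cross-reference. This is therefore a conflict between two rules, not a broken promise about end dates.
- Drugs that had stopped before the injection are classed correctly. A misclassified drug still appears as prior and in the listings.
- No efficacy model uses this status, and the SAP describes no analysis of medication duration, so an end date before a start date alters no stated output.
- The SAP refers to analysis-dataset specifications for other safety variables, which are not among the documents. They might handle this case differently, but the SAP text gives no correction.

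What remains is the classification itself. No other text in the SAP overrides the rule.

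**Conclusion.** The rule is wrong as written, and the consequence is minor. For a drug started before treatment, with the injection on day 2 or later and the end day missing in the treatment month, true use at the injection is always turned into prior-only status. The result is understated concomitant use in the descriptive Safety-population summaries, plus some end dates that precede start dates for drugs begun after treatment.

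The documents do not say how many records are affected. With 36 subjects planned and a single treatment month for each, the number is probably small. The percentages in the working describe the rule on an assumed uniform calendar and do not predict the data. The primary analysis is unaffected, and no effect on the per-protocol set is shown. The conclusion rests on reading the end-date sentence literally with the definitions in SAP 5.4.

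**What to change.** In SAP 5.5.2, set a missing medication end day to the last day of the recorded month, capped at the subject's end-of-study date. Add that a drug is concomitant unless the partial date shows that it stopped before treatment. This agrees in direction with the treatment-month rule for adverse-event onset. It also prevents an end date before a start date within the same month.

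The cost is a sentence or two in the SAP and a small change to the derivation. Some drugs stopped earlier in the treatment month will be counted as concomitant (48.4% of day pairs on the uniform grid), an error on the cautious side. The change should be made before the randomization code is broken, because Protocol Appendix V allows no SAP amendment after that.

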#### Missing severity or relationship to study treatment/study procedure of an AE

If the intensity of an AE is missing, an intensity of “severe” will be imputed.

If the relationship to study treatment/study procedure is missing, a relationship of “probable” will be imputed.

#### Missing/Partial End Date for Other Safety Variables

For other safety variables a similar approach for missing end dates will be followed in the data derivation of the Analysis Data Model (ADaM) specifications.

The same approach will be undertaken for the imputation of missing/partial end dates related to prior and concomitant treatments.

## **6. ANALYSIS SETS**

### **6.1 INTENTION-TO-TREAT**

The intent-to-treat population will consist of all subjects who are randomized and receive the actual study treatment (GS010). This population will be the population for the primary efficacy analysis.

## 6.2 PER-PROTOCOL POPULATION

The per-protocol population (PP) will consist of all subjects who are randomized, receive the actual study treatment (GS010 and sham treatment) and complete the week 48 ETDRS assessment without any major protocol deviation. This population will be the population for the supportive analysis of primary efficacy analysis.

## 6.3 SAFETY

The safety population is defined as those subjects who received study treatment (GS010). This population will be used as the population for all safety analyses.

# 7. INTERIM ANALYSES

An interim analysis is not planned for this study.

## 7.1 TIMING OF PRIMARY ANALYSIS

Primary endpoint analysis will be performed as soon as the last subject completes the Week 48 assessment and data are cleaned. At that point, all subjects will be recruited and followed for at least 48 weeks except in case of premature withdrawal. Many subjects will have reached Week 96 but not all of them. The study will be formally unmasked for the efficacy analysis at Week 48. The study will still continue up to scheduled end (Week 96). Although the study will have been unmasked for the study statistician, every effort (see Appendix V in Section 20.5 of the V3.0 protocol) will be invested to maintain the masking of subjects and personnel in charge of the conduct of the study including study managers, data managers, CRAs, investigators (except international coordinating investigators per Appendix V in Section 20.5 of the V3.0 of the protocol).

**Data Safety Monitoring Board (DSMB):** An independent DSMB will be constituted and responsible for periodically reviewing study data to assure the continued safe conduct of the study. The DSMB will meet to review the data at least every 6 months. Operational and logistical details will be provided in a separate DSMB charter.

# 8. DATA REVIEW

## 8.1 DATA HANDLING AND TRANSFER

Details regarding the data handling and data transfer process can be found in the PRA Clinical Informatics Plan.

## 8.2 DATA SCREENING

Beyond the data screening built into the PRA Data Quality Plan, the PRA programming of analysis datasets, tables, figures, and listings (TFL) provides additional data screening. Presumed

---

data issues will be output into SAS logs identified by the word “Problem” and extracted from the logs by a SAS macro and sent to Data Management.

Review of a pre-freeze TFL run on clean subjects and a post-freeze TFL run on the frozen database allow for further data screening prior to lock. The post-freeze TFL at Week 48 will be discussed with GenSight in a masked data review meeting to identify any final data issues and seek corrections prior to data-base lock. The PRA statistician and GenSight must approve database lock. The same procedure will be performed before the W96 database lock.

## 9. STATISTICAL METHODS

All analyses will use SAS version 9.4 or higher.

Unless otherwise noted, categorical variables will be summarized using counts and percentages. Percentages will be rounded to one decimal place, except 100% and 0% which will be displayed without any decimal places.

Continuous variables will be summarized using the number of observations (n), mean, standard deviation (SD), median, first quartile (Q1), third quartile (Q3), minimum and maximum. Minimum and maximum will be rounded to the precision of the original value.

Rounding rules are generally as follows:

- If the original value has 0 decimal places: mean, median, SD, Q1, Q3 and 95% confidence intervals (CIs) have 1 decimal place.
- If the original value has 1 decimal place: mean, median, SD, Q1, Q3 and CIs have 1 decimal place.
- If the original value has 2 or more decimal places: mean, median, Q1, Q3, CIs, and SD have the same decimal places as the original measure, up to a maximum of 3 decimal places.
- P-values will be presented as four decimal places.

Summary TFLs will be in landscape orientation and display standard headers containing the sponsor name (“GenSight Biologics”) as well as a standard footer containing the name of the program used to generate the display, its path, and a date/time stamp. Headers, footers, titles, and column headers for tables will be repeated on every page of each display; pages will be numbered “Page x of y.” Visit labels in tables and figures will show visit name. Summary TFLs containing no applicable data will display a line reading, “No applicable data were reported” or similar language. Dates and times will be presented using the DDMONYYYY HH:MM format. Summary TFLs will be produced using SAS® Output Delivery System (ODS) to generate rich text format (RTF) files and/or PDF files, if necessary. The default font will be 9-point Times New Roman, and minimum margins will be top 1”, bottom 1”, left 1”, right 1” (US letter). Standard indentation for subheadings is 2 spaces, and standard footnote indicators will be lowercase letters (e.g., a, b, c). Individual files will be named with the table, figure, or listing number plus the program name (with more descriptions related to output), concatenated with

underscores and using leading zeros as necessary for alphabetical sorting (e.g., T\_14\_1\_1\_disp). Listings will be sorted by location (Right/left), treatment and subject number if appropriate. For the listings where location and treatment are not appropriate, listings will be sorted by subject number only.

## 9.1 SUBJECT DISPOSITION

The number and percentage of subjects, who were screened, randomized, treated in the study, who completed the study, and the number of subjects who completed the Week 48 visit will be presented, together with the number and percentage of subjects who withdrew from the study prematurely and a breakdown of the corresponding reasons for withdrawal. The withdrawal data will be presented overall, as well as presenting withdrawal before Week 48 and withdrawal after week 48. This data will also be listed according to the eCRF. The number and percentage of subjects in ITT, PP and safety population will also be presented.

Week 48 data will be analyzed for the ongoing studies. The listing per subject of frozen visits (up to W48) will be presented along with status 'ongoing' for unfrozen visits. Once the individual listing is presented, all the data up to week 48 will be frozen and not disclosed. No data beyond week 48 will appear in the listing up until the data of all visits up to Week 96 is frozen. A table summarizing number of subjects with frozen data at each visit will also be presented.

Number of subjects who missed visits among the subjects who attended a particular visit will be presented. In addition, number of missing data for visual acuity and important SD-OCT parameters will also be summarized.

